The proposed study has two primary goals and each goal has an associated study phase. The primary goal of **Phase 1** is to augment the effects of post-retrieval propranolol observed in the R21. To achieve this goal, participants will receive 40 mg propranolol, 80 mg propranolol, (immediate release) or placebo immediately following each of two, retrieval CCE sessions in which exposure to standardized cocaine stimuli will serve to retrieve/reactivate memories for learning that subserves cocaine craving and cue reactivity (see figure 3). The two retrieval CCE session will be completed 24-hours apart and will be followed, two days later, by a third unmedicated test/follow-up CCE session. This two-day interim period will allow for the complete clearance of propranolol; Participants will be compensated \$75 to remain abstinent during this period. Multiple assessments of craving and physiological reactivity will be obtained at baseline and after stimulus presentations in all three CCE sessions (content and timing of stimulus

presentation in each session are detailed below in the Procedure section below). Participants will remain in MUSC's CTRC on the evening of each of the propranolol treated retrieval sessions of Phase 1 to prevent drug use.

The primary goal of **Phase 2** will be to assess the effects of post-retrieval propranolol on indices of cocaine use obtained over a 6-week follow-up in which abstinence is no longer reinforced. Drug use will be retrospectively evaluated during weekly interviews using a calendar-based assessment and urine drug screens will be performed 3 times each week to provide an objective assessment of drug use/abstinence. At week 1, 3 and 6, laboratory-based test/follow-up CCE sessions (similar to identical to the test CCE session in Phase 1) will permit (a) continued assessment of the maintenance of treatment effects on craving and cue reactivity to cocaine cues, and (b) assessment of generalization of DoR effects to novel cocaine picture cues (detailed below in the procedure section).

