As in the R21, urn randomization will be used in assigning participants to the two propranolol groups (40PP & 80PP) and the placebo group (PBO)⁶⁸ while balancing treatment assignment on two variables. To maximize the power for a comparison of effect across gender and minimize confounding, gender will be balanced during the randomization. Dollar amount of cocaine use at baseline (pre-study involvement) is a likely prognostic factor on craving and other outcome measure and will be controlled during randomization. Specifically, the total dollar amount of cocaine use in the 3 months prior to study involvement will be determined (using the Timeline Follow-Back) and the following binary urn variable will be used: Participants with \leq \$1000.00 cocaine use pre-study involvement vs. participants with $>$ \$1000.00 cocaine use pre-study involvement. The effects of additional factors such as age and duration of use will be statistically controlled during the analysis (if necessary, see Data Analysis Plan below) since further stratification of the randomization could yield some stratum with very small expected sample sizes. This could lead to significant imbalance in the overall study.

Medication Administration

Immediately following the completion of the cue exposures in each of the first two retrieval CCE sessions (described below), one of three medications will be administered in accordance with randomization; 40 mg of immediate-release propranolol, 80 mg of immediate-release propranolol or a matching placebo will be administered. Medications will be compounded, packaged and dispensed by the MUSC Investigational Drug Service (IDS), who will also oversee the randomization procedures for the study and record the treatment assignment. The IDS provides 24-hour, seven-days-a-week, on-call availability to randomize, enroll, dispense medications and unblind as necessary.

D. Phase 1 Laboratory Session Procedures

Verification of Abstinence

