Participants will be informed that they will be expected to remain abstinent from cocaine and other drugs for the 72-hour period preceding their CTRC admission in order to minimize the impact of recent drug/alcohol use on cue reactivity and minimize any potential for interaction between propranolol and cocaine/alcohol. Participants will be asked to come in the day before CTRC admission for a urine drug screen. If an individual tests positive for drugs or alcohol on admission day and/or the day before admission day, their admission will be rescheduled and they will not be compensated for that visit. If participant shows signs of intoxication/withdrawal (elevated blood pressure, diaphoresis, etc.), they will also be rescheduled. Individuals who test positive for substance use will be provided transportation to their residence (taxi service) if friends or relatives are unable to meet this need.

Session Preparation

Upon arrival at the CTRC at approximately 9:00 am, the participant will give breath and urine samples to assess abstinence for alcohol and other substances (as well as pregnancy for females). Observed urine drug screens in which a research assistant will monitor urine collection may be done at all required abstinence visits to minimize tampering with urine specimen. If the abstinence assessment is negative (see above, if positive), they will remain at the CTRC lounge until 9:30, at which time study personnel will escort them to the cue reactivity laboratory. Over the course of the two-day inpatient stay at the CTRC, nicotine patches will be provided to smokers, thereby reducing the risk of nicotine withdrawal during the cue exposure procedure. During the next half hour, a blood pressure cuff will be placed on the participant's arm and leads/sensors will be affixed, as described below, for the purpose of collecting HR and SC data. Participants will also complete a few assessments at this time (e.g., State Trait Anxiety Inventory or STAI, BDI, CSSA described below). Since all of these tasks will be accomplished in 5-10 min, participants will remain seated quietly for the remaining 20 min period. This waiting period serves to acclimate the participant to the laboratory setting (our research group has found acclimation to produce more stable baseline measures in several laboratory studies).

Cocaine Cue Exposure (CCE): Stimuli and Procedures

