Our research group has previously used this type of picture-based cue exposure procedure to successfully elicit craving in methamphetamine dependent individuals.^{69,70} Additionally, previous research by our group has shown that these pictures (subset of 10) elicit greater cocaine craving and subjective arousal in cocaine dependent individuals ($n = 27$; craving $\bar{x} = 5.9$ and arousal $\bar{x} = 10.1$) than in non-cocaine dependent controls ($n = 28$; craving $\bar{x} = .06$ and arousal $\bar{x} = 5.3$; both t 's > 3.6 , both p 's $< .001$). Furthermore, the mean craving and arousal reported by cocaine dependent individuals in response to the cocaine pictures was greater than the mean craving and arousal they reported in response to a set of neutral comparison pictures (craving $\bar{x} = 1.0$ and arousal $\bar{x} = 5.3$; both t 's > 4.5 , both p 's $< .0001$). Thus, we are confident these cocaine picture cues will serve as effective elicitors of craving and arousal in proposed study.

Procedure: At approximately 10:00 am, baseline subjective and physiologic outcome measures will be collected. Thirty minutes later, participants will receive the first sequence of CCE. Each sequence will consist of a 5-min video cocaine cue presentation followed immediately by in vivo cue presentation. Heart rate and SC data will be continuously collected during the first 50 sec of each cue type (video and in vivo). The CDMS Scale and BP will be obtained at the end of the in vivo cues. After the latter measures were obtained participants remained comfortably seated until the second, identical sequence of CCE commenced (approximately 5-10 min later). At the end of the CCE in the retrieval session, participants will receive their medication and complete all outcome measures. As indicated in figure 4, all dependent measures will be obtained immediately after CCE sequence and at 15 min. and 30 min. time points following termination of CCE. At the end of each retrieval session, research staff assisted the participant in removing the HR/SC leads and BP cuff. Participants will remain at the CTRC laboratory facility for an additional 60 min., at which time a blood draw will occur. The sample will

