be used to determine plasma concentrations of the propranolol so that the association between propranolol level and treatment effects can be assessed; the timing of the blood draw was based on the observation that peak concentrations of propranolol are reached 90-min post administration.^{52,53} Also at this time, participants will be asked to complete a dual-item form that asks whether or not they thought they received propranolol or placebo and, for those who

Figure 4

thought they received propranolol, at what dose level (this data will be used to assess the effectiveness of the blind). Research staff will then escort the participant to a research dedicated hospital room where they will remain overnight. The second retrieval cue exposure session, occurring the following day at the same time, will be identical to the first in all respects, including the overnight stay at the Institute of Psychiatry (IOP). Prior to discharge from the IOP the next day, research staff will schedule a test/follow-up CCE session, remind the participant that it is important to maintain abstinence during the interim period between their inpatient stay and the test/follow-up session and also remind them that a significant portion of the compensation (i.e., \$75.00) available at the end of the test session will be contingent on a negative UDS. Our group has previously used a

modified version of the ‘fishbowl’ contingency management (CM)⁷¹ procedure to successfully achieve an 80% rate of UDS verified cocaine abstinence over a 3-day period. Since the ‘fishbowl’ CM procedure only offered a small probability of earning the level of monetary compensation we plan to guarantee in the proposed study, we expect the abstinence rates during the 2-4 day interim period to exceed 90%.

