Follow-up Assessment Sessions: The goals of the follow-up visits are to determine if (a) the effects of post-retrieval propranolol on craving and cue reactivity to both familiar and novel cocaine cues are sustained over the 6-week follow-up, and (b) the post-retrieval propranolol treatment(s) impact cocaine use (variously measured) during follow-up. There will be a total of 18 visits scheduled over 6 weeks, with three visits occurring per week. All follow-up visits will begin with a drug/alcohol assessment. Briefly, participants will meet research staff at MUSC’s CTTC at approximately 9:00 a.m. on the pre-arranged day. At this time, a UDS and breathalyzer measurement will be obtained; cocaine, alcohol and other drug use status will be recorded. Next, research staff will perform a Timeline Follow-Back in order to ascertain the level of drug/alcohol use during the days since their last study visit. On follow-up visits that occur at the end of weeks 1, 3 and 6, participants will undergo a CCE session that is identical to the test session described above (test/follow-up CCE will follow drug/alcohol assessment). On these occasions, the cue exposures procedures will commence at approximately 10:30 a.m. to ensure that all study CCE sessions are being performed at approximately the same time of day (thereby serving to minimize the impact of circadian variation in sex and stress hormone levels on outcomes). Following CCE administration, the participant and staff will confirm the next appointment times and the appropriate level of compensation provided (see compensation plan below). At the end of each week, all appointments for the ensuing week will be scheduled. At the conclusion of the 6-week follow-up period, participants will be asked if they would like referrals for treatment

F. CCE Session Instruments and Related Measures

Self Report Measures

State-Trait Anxiety Inventory (STAI): The STAI is a 20-item self-report scale⁷² employing a Likert-scale format with four responses per item (1-4). Ten of the STAI items measure feelings of stress and anxiety, while the remaining ten items measure feelings of relaxation.

Cocaine Selective Severity Assessment (CSSA): The CSSA is an 18-item interview-based measure⁷³ of cocaine withdrawal symptom severity (e.g., lethargy, sleep disturbances, lethargy). It will be used to assess the association between withdrawal symptom severity and treatment response.

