Beck Depression Inventory (BDI): The BDI is a 21-item scale⁷⁴ that is a gold standard for the self-report assessment of depressed mood. The BDI will be administered at the screening visit and last study visit.

Adverse Events Form (AEF): We have used this instrument in many of our past to assess medication side effects/adverse events. The AEF will be administered at all study visits (i.e., end of inpatient stay and all test/follow-up visits).

Craving/Distress/Mood States (CDMS) Scale: This scale is a modified version of the Within Session Rating Scale^{75,76} and was used in the R21 and in several past^{77,78} and ongoing cue-reactivity protocols by our group. This self-report assessment contains thirteen, 100 mm visual analogue scales, with each being anchored by the adjectival modifiers “not at all” (left side of scale) and “extremely” (right side of the scale). The craving item asks the participant to rate the desire to use cocaine “right now”. The remaining items assess other drug-related subjective states (withdrawal, anxiety, frustration, anger, depressed mood, etc.). Figure 4 shows the timing of administration of this scale within the CCE sessions.

Cocaine Craving Questionnaire- Brief (CCQ): The CCQ is a 10-item scale used to assess the participant's feelings and thoughts about using cocaine at that moment in time. This will be assessed at the end of CCE sessions.

Physiological Measures

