Heart rate (HR), blood pressure (BP) and skin conductance (SC) were measured as indices of physiological arousal during each CCE session. Heart rate was collected via two electrodes, with one affixed to the right shoulder and the other on the bottom left side of the participant's ribcage. Blood pressure was measured using an intermittently inflatable cuff. Because this measure cannot be obtained unobtrusively, it will be taken at the same time as the CDMS is obtained (see figure 4 above). Skin conductance was recorded using Ag/AgCl electrodes attached to the skin over the metacarpal bone of the fifth digit, non-dominant hand. Since physiological arousal/reactivity was likely to be greatest in the earliest portions of a CCE sequence, HR and SC data will be continuously collected during the initial 50-second epoch of each video and in-vivo cue presentation and during the first 50-sec of the novel picture-based CCE (they also are collected at baseline and at 15-min and 30-min follow-up time points; see figure 4). The HR and SC signals will be amplified using the ECG 100c and GSR 100c Modules of the Biopac MP100 data acquisition system; the Biopac system will be interfaced with an Apple (MacBook Pro) laptop for data storage and subsequent reduction. While the HR, BP and SC measures obtained in the second medicated retrieval session may be impacted by the medication (not in the first retrieval session since the medication is administered after the CCE), it should be noted that these responses are not relevant to the evaluation of any hypothesis. Nonetheless, these responses will likely provide some measure/indication of the effects of the first medicated retrieval.

G. Participant Compensation

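### As its schedule is written, the Adverse Events Form is first completed after both doses, so side-effect reports have no pre-drug baseline and no form is completed before re-dosing (minor)

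*Combined protocol and SAP*

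**What the plan says.** The AEF is described in Approach section F as the instrument for medication side effects and adverse events. Its timing is given in one sentence: "The AEF will be administered at all study visits (i.e., end of inpatient stay and all test/follow-up visits".

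The doses are placed by three other statements:

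- Design Overview: "The two retrieval CCE session will be completed 24-hours apart".
- Medication Administration: study drug is given "Immediately following the completion of the cue exposures in each of the first two retrieval CCE sessions".
- Phase 1 Procedure: "The second retrieval cue exposure session, occurring the following day at the same time, will be identical to the first in all respects". Session 2 is followed by a second overnight stay, with discharge the next day.

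The plan also schedules other observations around the doses. Before each session, "Participants will also complete a few assessments at this time (e.g., State Trait Anxiety Inventory or STAI, BDI, CSSA described below"). During and after each session, "all dependent measures will be obtained immediately after CCE sequence and at 15 min. and 30 min. time points following termination of CCE". Screening includes a medical history, physical examination, electrocardiogram and blood chemistries (General Assessment). Anyone showing signs of intoxication or withdrawal at admission is rescheduled (Verification of Abstinence). Physicians monitor medical stability, and participants are taught the side effects of propranolol and followed in a staffed unit (Protection of Human Subjects).

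**The concern.** If the list in the AEF entry is taken at its word, nobody completes a side-effect form until both doses have been given. Two things are then lost.

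The first is a baseline. Participants are admitted after 72 hours of required abstinence, and some will have complaints before they take any study drug. With no pre-dose form, such complaints may be recorded later as adverse events. This should be about equal across randomised arms, so it adds noise to the safety table rather than bias. It does blur the tolerability comparison between 40 mg and 80 mg, and the plan notes that no human study of this kind has yet compared 40 mg with a higher dose.

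The second is a structured check before re-dosing. No form puts complaints arising after dose 1 in front of the monitoring physician before dose 2. Assigning an event to dose 1 or dose 2 then depends on recall, unless the form records onset. The form is not reproduced, so that cannot be told.

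**Working it through.** The plan gives no count of AEF completions, so there is no figure to reproduce. The check is a timeline and a count.

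**Clock time of the doses.** Phase 1 Procedure puts baseline at about 10:00 and the first cue sequence 30 minutes later. Each sequence is 5 minutes of video plus 5 minutes of in vivo cues, with 5 to 10 minutes between sequences. Cues therefore end at 10:30 + 10 + (5 to 10) + 10 minutes = 10:55 to 11:00. Take dose 1 at about 11:00 on day 1 and dose 2 at about 11:00 on day 2.

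**First AEF as written.** Discharge is on day 3, at a time the plan does not give. Assume 08:00 to 16:00.

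- After dose 1: 48 + (8 − 11) = 45 h, to 48 + (16 − 11) = 53 h.
- After dose 2: 24 + (8 − 11) = 21 h, to 24 + (16 − 11) = 29 h.

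That the form follows both doses needs no assumption, because discharge follows dose 2.

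**First AEF after dose 1 with the fix.** A form at 9:00 to 10:00 on day 2 falls 22 to 23 h after dose 1 and 1 to 2 h before dose 2.

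**Completions per participant.**

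- Narrow reading: discharge + first test session + weeks 1, 3 and 6 = 1 + 1 + 3 = 5.
- Broad reading: discharge + first test session + all Phase 2 visits = 1 + 1 + (6 × 3) = 20.

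| Period | AEFs now | AEFs with fix | Other scheduled cover |
|---|---|---|---|
| Before dose 1 | 0 | 1 | Screening work-up; STAI and CSSA; withdrawal and abstinence check; heart rate (HR), blood pressure (BP) and CDMS in session 1 |
| Between doses | 0 | 1 | See count below |
| After dose 2 | 5 (or 20) | 5 (or 20) | Later session measures and visits |
| Total | 5 (or 20) | 7 (or 22) | |

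**Cover between the doses.** Session 2 repeats session 1, so the count is:

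- BP and CDMS sets: day 1 at 15 and 30 min (2), plus day 2 baseline and after the first sequence (2) = 4. The set after the second sequence falls at about the time of dosing on each day, so the total could be 6.
- HR readings: day 1 at 15 and 30 min (2), plus day 2 baseline (1), plus two video and two in vivo epochs (4) = 7.
- STAI 1, CSSA 1, blood draw and treatment-guess form about 90 minutes after dose 1. Side-effect forms: 0.

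**What that cover can and cannot do.** HR and BP bear directly on bradycardia and hypotension, the two risks named in the dosing rationale. On day 1, however, the scheduled readings stop 30 minutes after the cues and the leads and cuff come off, whereas the plan puts peak concentration at about 90 minutes. The CSSA measures withdrawal and the CDMS includes a withdrawal item, so withdrawal complaints do have a baseline before dose 1. Neither is described as asking about side effects.

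**The case against.** The strongest case against has four parts.

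1. **It may be a wording slip.** The sentence begins with all study visits, and Participant Compensation numbers the first test session as visit 3, which makes the retrieval days visits 1 and 2. They may have been meant. This stands as a possibility, but the list that defines the phrase leaves them out. At the least, that list needs correcting.

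2. **The likeliest pre-existing complaints are already captured.** Withdrawal is assessed by the CSSA and CDMS before dose 1, and people with visible signs are rescheduled. This stands, and it narrows the baseline gap to complaints that those instruments do not record.

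3. **A form before dose 2 could disturb the intervention.** Dosing must follow the cues at once, because the treatment is defined by that timing. This stands against any form placed between the cues and the dose, which is why the fix does not put one there.

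4. **The change comes late.** The text describes recruitment as near its end. This also stands: only remaining participants would benefit, and adverse-event collection would differ between earlier and later participants.

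A reader might go further and infer that participants are re-dosed without safety monitoring. The documents do not support that: clinical staff, vital signs and a screening work-up are all in place. Nor do they support an inference that the efficacy results are at risk. The Data Analysis Plan uses no AEF data in any hypothesis test, and the placebo arm keeps the between-arm comparison of events valid.

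**Conclusion.** The point holds in a limited form and is minor. As the AEF entry is written, no side-effect form is completed before dose 1 or between doses: 0 of 5 scheduled completions (or 0 of 20) precede dose 2. The shortfall is in the baseline for side-effect reporting and in a structured check before re-dosing. It is not in safety monitoring as a whole, and it affects no hypothesis test.

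The conclusion rests on reading the list in the AEF entry as complete and on the absence of any other AEF schedule in the documents. The 45 to 53 hour figure also rests on the assumed discharge time. The documents give no adverse-event rate and do not show the form, so the effect on event counts cannot be sized.

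**What to change.** In the AEF entry, add the existing form on both retrieval days, in the session-preparation period (about 9:00 to 10:00) and before any cue exposure. Complete it before the 20 minutes of quiet sitting so that acclimation is kept. Pass the day 2 answers to the physician already monitoring medical stability before dose 2 is given. Place no form between the cues and the dose. Keep the later AEFs.

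Add one line to the Data Analysis Plan: report events as new or worsened since the day 1 form, by arm. Identify participants enrolled before the change, who have no such baseline. If the retrieval days were always meant to be included, correct the list to say so.

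Cost: two short forms per remaining participant and no extra visit. The upper bound is 2 × 200 = 400 forms. The number still to enrol is not given; if it were only the 20 added when the target rose from 180 to 200, the cost would be 2 × 20 = 40 forms.

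There is a small chance that asking about side effects primes the session 2 measures and the day 2 treatment guess. The plan says the session 2 physiological responses bear on no hypothesis, though "these responses will likely provide some measure/indication of the effects of the first medicated retrieval", and session 2 differences enter only a secondary analysis. Participants are in any case taught the side effects of propranolol, so the added prompting should be slight.
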